| 
Investigational Medicinal Product: dose/mode of administration/ dosing schedule Test: 1200 mg of Cisticid new formulation (two 600 mg tablets), single dose administered orally in fed condition
 |
| 
Reference: 1200 mg of Biltricide (two 600 mg tablets), single dose administered orally in fed condition in two periods.
 |
| 
Planned trial and treatment duration per subject: Screening period of maximal 28 days,
 |

Three weeks dosing period including washout followed by one week of clinical follow-up.

Statistical methods: Statistical analysis will be performed using the computer program package SAS® System PPD . If not stated otherwise, the level of statistical significance will be $\alpha=0.05$. PK data evaluation will be performed based on standard non-compartmental methods using the validated software tool PPD . Details on the statistical analysis and PK data analysis will be presented in the statistical analysis plan prior to database lock.

The statistical analysis will not be started until all data have been corrected and checked for plausibility and until all necessary coding and assessments have been completed.

The analysis of the primary endpoints AUC_{0-t} and C_{max} of L-PZQ will be performed using the PK population. Both parameters will be log-transformed before analysis. For the demonstration of bioequivalence different approaches will be applied for AUC_{0-t} and C_{max} . For AUC_{0-t} the standard approach will be followed, i.e. the point estimate and the 90% CI of the Test/Reference geometric mean ratio must fall within [0.80, 1.25]. A linear mixed-effects model will be applied for the analysis of AUC_{0-t} . The treatment difference TEST – REFERENCE will be estimated, and the 90% CIs for the difference will be calculated. The difference and 90% CIs will be back-transformed to the original scale. If the 90% CI for the ratio (test/reference) lies entirely within the interval [80.00 – 125.00], then the BE criterion is fulfilled for AUC_{0-t} .

For the analysis of C_{max} , a reference-scaled bioequivalence approach will be applied.

Substance Code
Protocol Number

Praziquantel
MS 200585-0002

Short title Praziquantel Bioequivalence Study

2 Sponsor, Investigators and Trial Administrative Structure

This clinical trial will be sponsored by:

Merck KGaA [name]

Committees

Ethics and Investigation
Committee :

PPD

Phone: PPD
Filing at PPD
PPD

Investigation Committee:

PPD

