8.4.2 Analysis of Primary Endpoints

The analysis of the primary endpoints AUC_{0-t} and C_{max} of L-PZQ will be performed using the PK population. For the demonstration of bioequivalence different approaches will be applied for AUC_{0-t} and C_{max} . For AUC_{0-t} the standard approach will be followed, i.e. the point estimate and the 90% CI of the Test/Reference geometric mean ratio must fall within [0.80, 1.25]. AUC_{0-t} of L-PZQ will be log-transformed and analyzed using a generalized linear model as given by the SAS code below:

```
PROC GLM DATA=PK;
```

```
CLASS SEQ SUBJ PER TRT;
```

```
MODEL LNPARAM = SEQ PER TRT SUBJ(TRT) / DDFM=SATTERTH;
```

LSMEANS TRT / ADJUST=T PDIFF CL ALPHA=0.10.

TEST H=SEQ E=SUBJ(TRT);

RUN;

QUIT;

The treatment difference TEST – REFERENCE will be estimated, and the 90% CIs for the difference in LS-means will be calculated. The difference and 90% CIs will be back-transformed to the original scale. If the 90% CI for the ratio (test/reference) lies entirely within the interval [80.00 – 125.00], then the BE criterion is fulfilled for AUC_{0-t} .

For the analysis of C_{max} , a reference-scaled bioequivalence approach will be applied as follows:

Point estimate and 90% confidence interval will be computed as described above for AUC. If $CV_{WR} \leq 30\%$ for C_{max} (i.e. the within-subject CV for the reference drug is $\leq 30\%$), then the common acceptance range for bioequivalence will apply. For $30\% < CV_{WR} \leq 50\%$ the acceptance interval will be widened according to $[U, L] = \exp [\pm k \cdot sWR]$, where U is the upper limit of the acceptance range, L is the lower limit of the acceptance range, k is the regulatory constant set to 0.760 and sWR is the intrasubject standard deviation of the log-transformed values of C_{max} of the reference product. sWR will be calculated using the data under reference treatment only. For all values of CV_{WR} greater than 50% the acceptance range is fixed to [69.84 – 143.19].

The geometric mean ratio for C_{max} should always lie within [80.00 – 125.00].

- a. Descriptive statistics and boxplots will be provided by treatment.

CCI

PROC GLM DATA=PK;

CLASS SEQ SUBJ PER TRT GROUP;

MODEL LNPARAM = SEQ PER TRT GROUP GROUP*TRT SUBJ(TRT) / DDFM=SATTERTH;

LSMEANS TRT / ADJUST=T PDIFF CL ALPHA=0.10.

TEST H=SEQ E=SUBJ(TRT);

RUN;

QUIT;

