6.3 Overall Trial Design and Plan

This randomized, open-label, single dose, a 3-periods and 3-sequences crossover design with a 7-day wash-out period.

The bioequivalence will be evaluated with primary endpoints are AUC0-t, AUC0-∞ or Cmax for enantiomers and racemic mixture of praziquantel.

The subjects will be randomized to one of the 2 treatment in 3 periods, 3 sequences (see table below). Ten subjects will be randomized to each treatment sequence with a minimum proportion of 30% for each sex in each treatment sequence.

Sequence	Period 1	ut I	Period 2	ut -	Period 3
PRR	Cisticid [®]	h-o-l	Biltricide [®]	h-o-i	Biltricide [®]
RPR	Biltricide®	/asl per	Cisticid [®]	/as per	Biltricide [®]
RRP	Biltricide®		Biltricide [®]		Cisticid [®]

7 Sample Size

The sample size estimation is based on the CV intrasubject variability of praziquantel.

The sample size is determined by the variability currently available, these values are 60 to 50 and 35% for Cmax and AUC, respectively. With this information, praziquantel is considered as a drug highly variable. In a clinical investigation realized by Merck Serono by a phase 1 design the variability obtained was 34.5% for L-praziquantel, 34.5% for AUC and 52% for Cmax.

The sample size calculation was realized using the PPD functions recommended by European Medicines Agency (EMA).

Considerations

- The reference-scaled average bioequivalence is applicable only for Cmax, for ABC apply the c conventional bioequivalence limits
- If the CVintrasubject value is greater than 50% the bioequivalence limits will be 0.70-1.43

Several assumptions were considered, there are:

- The real mean of ratio test/reference for primary pharmacokinetic parameters.
- Cmax CVintra subject reference: 45-55%
- Cmax CVintra subject test: 45-55%
- AUC CVintra subject reference: 39.5%
- AUC CVintra subject test: 39.5%
- Alpha value: 0.05
- Power 80%
- Droup-out rate: 20%

CCL

With all these assumptions the sample size required is 48 healthy subjects are needed to obtain power greater of 80%, neverthless considering the 20% of rate droup-out the sample size needed to avoid this problem is 60 subjects.

The 60 subjects going to be randomized into 3 sequences for each treatment, for this reason 20 subject will be enrolled in each treatment sequences.

8 Overview of Planned Analyses

PK parameters will be performed using PPD

Statistical analysis will be performed using SAS 9.4.

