Descriptive statistical methods will be used to summarize demographic characteristics, pharmacokinetics parameters and adverse events. After the data base closing

Individual plasma concentration-time will be tabulated and plotted. Primary pharmacokinetics parameters, AUC and Cmax, will be tabulated and plotted by subject. Likewise, differences and odd ratios for test/reference will be tabulated for each subject for those parameters. Plasma concentration - time graphs will be made using arithmetic and semi-logarithmic scale. All de calculations will be determinated in concordance with NOM-177-SSA1-2013

Bioequivalence test methodology will be perform using the next codes: PRC GLM DATA=PK CLASS SEQ SUBJ PER TRT; MODELLNPARAM=SEQ PRE TRT SUBJ(TRT)/DDFM=SATTERTH; LSMEANS TRT/ADJUST=T PDIFF CL ALPHA=0.01. TEST H=SEQ E=SUBJ(TRT); RUN; QUIT;

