8.1 Interim Analysis

Bioequivalence for AUC:

A mixed model will be applied to log-transformed AUC0-t and AUC0-∞ with treatment, period and sequence as fixed effects, and subject (sequence) as a random effect. Based on the residual error term 90% confidence intervals will be computed for the estimated differences Test − Reference, resulting in 90% confidence intervals for the Test/Reference ratios after backtransformation.

Bioequivalence for Cmax:

The 90% confidence intervals will be computed for the estimated differences Test – Reference. If $CV_{WR} \leq 30$ the procedure to estimate is the same as the confidence intervals for AUC, if $30\% < CV_{WR} \leq 50\%$, the acceptance interval will be widened according to the next formula (U, L) = $\exp(\pm k'sWR)$, where U is the upper limit, L is the lower limit, k is the constant established as 0.760 and sWR is the intrasubject standard deviation for the Cmax log transformated value for reference product. For values greater than 50% the aceptace range going to be 69.84 – 143.19

TO evaluate the group effect, the next codes will be used: PROC GLM DATA=PK

CLASS SEQ SUBJ PER TRT GROUP;

MODEL LNPARAM=SEQ PER TRT GROUP GROUP*TRT SUBJ(TRT)/ DDFM=SATTERTH;

LSMEANS TRT/ ADJUST=T PDIFF CL ALPHA=0.10.

TEST H=SEQ E=SUBJ(TRT);

RUN;

QUIT;

Statistical analysis for secondary parameters

The secondary pharmacokinetics parameters (Tmax, AUCextrapolated, t½, Cl/F and Vd/F) going to be analyzed by descriptive statistics

9 Changes to the Planned Analyses in the Clinical Trial Protocol

The statistical methods as described in the protocol were adopted.

There are no changes to the planned analyses.

10 Protocol Deviations and Analysis Sets

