10.1 Definition of Protocol Deviations and Analysis Sets

All deviations should be justified with statistical or scientific data and any change to the original statistical plan should be documented, in the study master file and in the pharmacokinetics statistical report as well as in the final study report. Subjects' data will not be replaced. Any missing data will be considered as non-existent data. Likewise, data cannot be removed from the statistical analysis, except in the following events.

Research Subjects with Pre-dose Concentrations in the Biological Matrix

In the event pre-dose concentration is < 5 % of the C_{max} value for a research subject, subject's data can be included without any adjustment to measurement and pharmacokinetic calculations. When pre-dose value is > 5 % of the C_{max} , research subject should be removed from all study bioequivalence assessments.

Exclusion of data due to vomit or diarrhea.

Data from research subjects who experience vomiting and diarrhea throughout the bioequivalence study for immediate release products can be removed from the statistical analysis if vomiting and diarrhea occur before 2 fold the median for t_{max} or 2 fold t_{max} value obtained from the research subject in a given period.

Research subject with very low plasma concentrations for study drugs.

As established by NOM-177-SSA1-2013, research subjects in a cross designed who provide evaluable data for test drug and reference drug, or who do not have evaluable data in the single period of a parallel design, should not be either included in the statistical analysis.

It is considered that a research subject has very low concentrations, if the AUC is lower than 5 % of the geometric means for the reference drug's AUC (it should be calculated without including outliers). Exclusion of data due to this reason will only be accepted prior scientific rationale and review of the case by the COFEPRIS.

11 General Specifications for Statistical Analyses

Pharmacokinetic parameters (non-compartmental analysis) and statistical analysis for determining bioequivalence will be calculated using Phoenix WinNonlin 8.0 software.

The results of this trial will be reported using summary tables, figures, and data listings, as appropriate. All data will be summarized by treatment and/or scheduled time point, as appropriate.

12 Protocol Deviations

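### The SAP's code for the bioequivalence test cannot run as printed and contradicts the SAP's own model, and the documents name two programs for the test

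*SAP*

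**What the plan says.** **Model in code.** Protocol 8.4.2 analyses log AUC with PROC GLM and the line "MODEL LNPARAM = SEQ PER TRT SUBJ(TRT) / DDFM=SATTERTH", at ALPHA=0.10. It computes the Cmax interval the same way. SAP section 8 repeats the step as "PRC GLM DATA=PK CLASS SEQ SUBJ PER TRT" followed by "MODELLNPARAM=SEQ PRE TRT SUBJ(TRT)/DDFM=SATTERTH", at ALPHA=0.01.

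**Model in words.** The protocol synopsis says "A linear mixed-effects model will be applied for the analysis of" AUC. SAP 8.1 (headed Interim Analysis, though it holds the main analysis) describes a mixed model "with treatment, period and sequence as fixed effects, and subject (sequence) as a random effect", with 90% intervals. Its code for the group effect returns to GLM: "MODEL LNPARAM=SEQ PER TRT GROUP GROUP*TRT SUBJ(TRT)/ DDFM=SATTERTH".

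**Program.** Protocol 8.3 assigns the bioequivalence determination to SAS. SAP 8 says "Statistical analysis will be performed using SAS 9.4". SAP 11 says "statistical analysis for determining bioequivalence will be calculated using Phoenix WinNonlin 8.0 software".

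SAP section 9 declares no change from the protocol's planned analyses.

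**The concern.** This code decides the trial: the 90% interval from it is compared with 80–125% for AUC and with the possibly widened limits for Cmax. A confirmatory specification should let a second statistician obtain the same interval without making choices. Here the printed step does not execute, the period term required by the SAP's own text is misnamed, the subject term in the code differs from the one in the text, and two programs are given the same task. A reader cannot tell from the documents which model and which program produce the verdict.

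**Working it through.** **1. The statements side by side**

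| Place | Model | Period | Subject | DDFM | Interval | Program |
|---|---|---|---|---|---|---|
| Protocol synopsis | mixed | not stated | not stated | – | 90% | SAS |
| Protocol 8.4.2 | PROC GLM | PER | SUBJ(TRT) | yes | ALPHA=0.10 | SAS (8.3) |
| SAP 8 | PROC GLM | PRE | SUBJ(TRT) | yes | ALPHA=0.01 | SAS 9.4 |
| SAP 8.1, text | mixed | fixed | subject(sequence), random | – | 90% | – |
| SAP 8.1, group code | PROC GLM | PER | SUBJ(TRT) | yes | ALPHA=0.10 | – |
| SAP 11 | – | – | – | – | – | WinNonlin 8.0 |

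**2. Does the SAP 8 step run?** No, for two independent reasons. PRE is in neither the CLASS list nor any definition, so the step stops unless the data set happens to hold a variable of that name, which would then be fitted as a covariate. DDFM belongs to the mixed-model procedures, and the MODEL statement of PROC GLM does not accept it. The second fault is in all four code blocks (two in protocol 8.4.2, one each in SAP 8 and 8.1), so falling back on the protocol code does not help. Run-together words and missing punctuation may come from file conversion and carry no weight here.

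**3. The plan's own figure.** Inputs from protocol 8.1: within-subject CV 39.5%, ratio 0.95, limits 0.80–1.25, one-sided alpha 0.05, 20% dropout. Within-subject variance = ln(1 + 0.395²) = 0.1450. For the three-sequence partial replicate with subject within sequence, Var(T−R) = 1.5 × 0.1450/N on 2N − 3 df. At N = 48 (93 df) the exact two one-sided tests power is 80.5%; at N = 45 it is 77.9%. And 48/0.80 = 60. The stated 48 and 60 reproduce.

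**4. What if period were really left out?** The documents give no period effects, so the sizes below are assumptions.

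- Residual df becomes 2N − 1 = 95, and the residual variance gains N × Σ(period effect − mean)²/95.
- A shift d in one period gives Σ = (2/3)d². For d = 0.10 the gain is 48 × 0.00667/95 = 0.0034, so 0.1450 becomes 0.1484.
- Power at N = 48 is 80.5% for no shift, and 80.3%, 79.6% and 76.9% for shifts of 0.05, 0.10 and 0.20. Treating the enlarged residual as the true variance slightly overstates the loss, because with balanced sequences the shift cancels from the estimate.
- Bias in T−R for a 0.10 shift is 0 with balanced sequences, 0.0009 log units at an assumed 20/20/19 split, and 0.0125 at an assumed 20/16/12 split.
- A harsher case uses the 59 subjects shown in SAP 15.5 and effects of −0.1, 0, +0.1: (0.145 × 115 + 59 × 0.02)/117 = 0.1526. The residual variance rises 5% and the interval widens about 3%. With −0.2, 0, +0.2: (0.145 × 115 + 59 × 0.08)/117 = 0.183, or 26% and about 12%.

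**5. The other faults in the same block.** ALPHA=0.01 read literally gives a 99% interval; power is then 39.6% at N = 48 and 55.5% at N = 59. SUBJ(TRT) gives each subject a separate effect under each treatment. The 144 observations at N = 48 then leave 144 − 98 = 46 residual df instead of 144 − 51 = 93; power is 79.9% if test and reference variances are equal.

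**6. Mixed or fixed subject effect?** The PK set requires parameters in all periods, so every subject has one test and two reference values and T−R is a within-subject contrast. With subject nested in sequence, simulated fixed and random versions gave the same estimate to rounding, and standard errors within 0.0000003.

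**The case against.** The strongest reply is that the intended analysis is not in doubt. SAP 8.1, the SAP group-effect code and both protocol blocks contain period, and SAP 9 declares no change, so PRE is a slip for PER. Deleting DDFM leaves GLM's ordinary residual df and involves no choice. With complete data, mixed and fixed subject effects agree once the nesting is right, and on one and the same model SAS and WinNonlin should also agree. Dropping period would mainly widen the interval, which makes a bioequivalence claim harder. Half-life is 0.8–3 hours, the washout is 7 days, and the diet is repeated, so large period effects are not expected; effects of ±0.2 imply a swing of 0.4 log units, about 49% (e^0.4 = 1.49).

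Most of this stands, and it removes any claim of a large numerical effect. It does not remove the contradiction. The code nests subject in treatment while SAP 8.1 nests subject in sequence; that changes the residual df and the data behind the error term, and cannot be put down to typing. The deciding program is stated in two ways. And no block in either document runs as printed.

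**Conclusion.** The point holds as a fault of specification: the confirmatory code in SAP 8 is not executable, it contradicts SAP 8.1, and the documents leave the subject term and the deciding program open. It should be corrected. The period term itself matters little: about 1 percentage point of power at N = 48 under an assumed 0.10 log-unit shift in one period, with no bias when sequences are balanced. Only much larger assumed period effects would matter.

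Two stronger readings are tempting and are not supported. One is that the SAP planned an analysis without a period effect. Its own text and every other code block include period, and a step that stops with an error fits no model at all. The other is that the reported result came from an improvised repair. The SAP is dated May 2019, after the planned trial period of December 2017 to January 2018, and SAP 15.2 already states equivalence. But neither document contains a program log or output from the model step, so what was actually run is unknown. The dates show only that a correction now would be written with data in hand, which is a reason to tie each element to text already in the documents.

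**What to change.** Use one executable model statement, identical in protocol 8.4.2, SAP 8 and SAP 8.1:

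- SEQ, PER and TRT fixed, and subject within sequence as in SAP 8.1. Any TEST line for sequence uses that same subject term as its error.
- A 90% interval: ALPHA=0.10, not 0.01.
- Either PROC GLM without DDFM, or a mixed-model procedure with DDFM kept. Bring the synopsis and the SAP 8.1 wording into line with the choice, and apply the same corrections to the group-effect code.

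Changing only PRE to PER and deleting DDFM is not enough, because ALPHA=0.01 and SUBJ(TRT) would stay in the SAP 8 block.

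Name SAS as the single program that decides bioequivalence. Limit WinNonlin in SAP 11 to PK parameters or to a check that cannot change the verdict. Rerun from the corrected code and report that run.

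Cost: a short SAP revision, a protocol clarification under the change process in protocol 10.5, and one rerun.

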8.1 Sample Size

Information on Praziquantel currently available to the WHO PQP Group indicated that the intrasubject variability for Praziquantel is around 50-60% for C_{max} and 35% for AUC, placing this compound in the highly variable drug class. The data from the Merck Serono phase I study performed recently, where Cisticid was used as comparator and different doses of PZQ ODT formulations were examined, confirmed this information and indicated for L-PZQ a CV% of 34.5 for AUC in the overall population and of 39.5% in non-whites, and a CV% for C_{max} of 52%.

The sample size calculation was performed using the R-functions `sampleN.RSABE` and `sampleN.TOST` of the package `PowerTOST`, which takes advantage of the reference-scaled approach suggested by the EMA.

Points to consider:

- For this clinical study comparison, the reference scaled approach is only applicable for C_{max} . For AUC conventional BE limits apply [0.80 – 1.25].
- In general, the reference scaled approach is applicable for $CV \leq 50\%$: For $CVs > 50\%$ fixed BE margins need to be used [0.70 – 1.43].
- Regulatory constant applied for reference scaled approach (EMA): 0.76

The following assumptions were made:

- Assumed true mean Test/Reference ratio for primary PK: 0.95
- C_{max} Coefficient of variation (Reference): 45 - 55%
- C_{max} Coefficient of variation (Test): 45 - 55%
- AUC Coefficient of variation (Reference): 39.5%
- AUC Coefficient of variation (Test): 39.5%
- One-side alpha: 0.05 (corresponds to 90% confidence level)
- Power: 80%
- Drop-out (DO) rate: 20% (agreed with CRO)

For this comparison the conventional BE margins [0.80 – 1.25] need to be applied for AUC. Therefore the rather high CV for AUC of L-PZQ determines the sample size for this trial. CCI

Together with the assumptions above, 48 evaluable subjects will provide 80% power to demonstrate BE. Taking a drop-out rate of 20% into account, 60 subjects should be randomized in this BE trial.

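### The SAP's main bioequivalence code requests 99% confidence limits, while the protocol and the rest of the SAP fix a 90% interval

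*SAP*

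**What the plan says.** SAP Section 8 introduces one block of SAS code as the method for the bioequivalence test. Its least-squares-means line reads "LSMEANS TRT/ADJUST=T PDIFF CL ALPHA=0.01".

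The other statements of the confidence level are:

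- **Protocol 8.4.2, code:** "LSMEANS TRT / ADJUST=T PDIFF CL ALPHA=0.10". The text of that section then judges AUC0-t by whether the 90% interval lies within 80.00–125.00, and has the Cmax interval computed the same way.
- **Protocol 8.1, sample size:** "One-side alpha: 0.05 (corresponds to 90% confidence level".
- **SAP 8.1, AUC:** "Based on the residual error term 90% confidence intervals will be computed". The Cmax paragraph also specifies 90%. (The section is headed as an interim analysis but describes the final one.)
- **SAP 8.1, group-effect code:** "LSMEANS TRT/ ADJUST=T PDIFF CL ALPHA=0.10".
- **SAP 9:** "There are no changes to the planned analyses".

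The SAP also names two programs. Section 8 says "Statistical analysis will be performed using SAS 9.4", and Section 11 says "statistical analysis for determining bioequivalence will be calculated using Phoenix WinNonlin 8.0 software".

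**The concern.** In SAS, `ALPHA=0.01` with the `CL` option gives two-sided 99% limits. Judging bioequivalence by whether those limits fall inside the acceptance range amounts to two one-sided tests at 0.005 each, not 0.05. The SAP therefore holds two contradictory levels for the interval that decides its primary question, and the wrong one sits in the only main-analysis code it prints.

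The same block has other slips, such as `PRC` for `PROC` and `PRE` for `PER`. Those stop the program or raise an error and so reveal themselves. The alpha value does not: once the rest is repaired, it would give 99% limits without warning.

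What is at stake is a wrongly failed trial: a product that meets the protocol's 90% rule could be reported as not bioequivalent. A smaller point concerns the record. SAP 15.2 says the results lie within the acceptance ranges, and the SAP does not show which program, at which level, produced the intervals behind that statement.

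**Working it through.** **Inputs.** From protocol 8.1: true test/reference ratio 0.95; AUC CV 39.5% for both products (34.5% in the overall population of the earlier phase I study); Cmax CV 45–55%; AUC limits 0.80–1.25; one-sided alpha 0.05; 48 evaluable subjects; 20% drop-out. From protocol 5.1: three sequences, three periods, reference given twice. From SAP 15.5: n = 59.

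**Formulas for AUC0-t, log scale.**

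- σ² = ln(1 + CV²) = ln(1 + 0.395²) = 0.1450
- SE = √(1.5 σ²/N), with 2N − 3 degrees of freedom
- Power is the probability that estimate ± t × SE lies within ln 0.80 to ln 1.25, integrated over the chi-square distribution of the residual variance.

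**Step 1: reproduce the plan's figure.** With 0.05 per side, N = 48 gives power 80.5% and N = 45 gives 77.9%. Then 48/(1 − 0.20) = 60. Both of the plan's numbers are recovered, so the trial was sized for the 90% interval.

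**Step 2: width of the interval.** At N = 48, SE = √(1.5 × 0.1450/48) = 0.0673, with 93 degrees of freedom.

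| Limits | t | Half-width | Interval at an observed ratio of 0.95 |
|---|---|---|---|
| 90% | 1.661 | 0.1118 | 0.849–1.062 (passes) |
| 99% | 2.630 | 0.1770 | 0.796–1.134 (fails at 0.80) |

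The ratio of widths is 2.630/1.661 = 1.58.

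**Step 3: power for AUC0-t.**

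| N | CV | True ratio | 90% limits | 99% limits |
|---|---|---|---|---|
| 48 | 39.5% | 0.95 | 80.5% | 39.6% |
| 59 | 39.5% | 0.95 | 87.7% | 55.5% |
| 60 | 39.5% | 0.95 | 88.2% | 56.7% |
| 59 | 39.5% | 1.00 | 95.5% | 70.5% |
| 59 | 34.5% | 0.95 | 93.9% | 71.6% |
| 59 | 34.5% | 1.00 | 98.8% | 87.6% |

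With N − 2 degrees of freedom instead, the second row becomes 87.3% and 53.3%, so that choice matters little. At 99% limits, 80% power would need 90 evaluable subjects.

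**Step 4: which observed ratios pass.** At N = 59 and CV 39.5% the half-widths are 0.1007 (90%) and 0.1590 (99%). The passing range runs from 0.80 × exp(h) to 1.25 × exp(−h): 0.885–1.130 with 90% limits and 0.938–1.066 with 99% limits.

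**Step 5: Cmax.** I simulated 200,000 trials per setting under the scaled rule: constant 0.760 applied to the reference standard deviation for CV 30–50%, fixed limits 69.84–143.19 above that, point estimate within 0.80–1.25, and true ratio 0.95. Ranges are over CV 45–55%.

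| N | 90% limits | 99% limits |
|---|---|---|
| 48 | about 95–96% | about 72–80% |
| 59 | about 98% | about 85–90% |

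**Step 6: direction.** At a true ratio of 1.25 and N = 48, the chance of wrongly declaring bioequivalence on AUC0-t is 5.0% with 90% limits and about 0.5% with 99% limits.

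**The case against.** The best case against is that this is a typing error with no consequence. Every other statement of the rule says 90%, SAP 9 says the protocol's methods were adopted, and the block is visibly mistyped. The line holding the alpha value itself ends in a full stop where SAS needs a semicolon, so a programmer would have to edit it with the protocol's code to hand. If WinNonlin produced the intervals, as SAP 11 says, the SAS setting never reached the decision.

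Moreover, the SAP is dated May 2019, after the planned trial period, and already reports that the results fall within the acceptance ranges. For the same model and data the 90% interval lies inside the 99% interval, and neither the acceptance limits nor the point-estimate rule depends on alpha. A pass at 99% is therefore a pass at 90%.

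Much of this stands. A slip is the likely explanation, and this point does not overturn the equivalence reported in SAP 15.2. The power figures describe what would have been risked if 0.01 had governed the decision, and nothing in the documents shows that it did. But none of this makes the printed setting right. SAP 5 says its analyses will go into the study report and regulatory submissions, so the level and the program behind the primary result should be unambiguous.

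**Conclusion.** The contradiction is real, and `ALPHA=0.01` is wrong as written. It should be fixed, although its direction is conservative. If it governed the decision, AUC0-t power under the protocol's assumptions would drop by about 41 percentage points at 48 subjects (80.5 − 39.6) and about 32 at 59 (87.7 − 55.5). In the most favourable case examined at 59 (CV 34.5%, ratio 1.00) it would drop by about 11 points (98.8 − 87.6). Cmax would lose less.

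These figures assume equal within-subject variance for test and reference, as protocol 8.1 does, and the ordinary within-subject crossover error, not the subject-within-treatment term printed in the code. The explicit link from alpha to the 90% interval comes from the protocol; the sample-size section of the SAP gives alpha as 0.05 without saying whether it is one-sided. That the setting is a slip is an inference.

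**What to change.** In the SAP Section 8 code, change `ALPHA=0.01` to `ALPHA=0.10`.

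Repair the rest of the block at the same time: `PRC`, `PRE`, the run-together `MODELLNPARAM`, the missing semicolon after `DATA=PK`, the full stop ending the least-squares-means line, and `DDFM=SATTERTH`, which is an option of `PROC MIXED` and not of `PROC GLM`. The full stop and the `DDFM` option also appear in the protocol's code. Some spacing faults may come from reading the PDF.

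Add one sentence stating that the decision interval for L-PZQ AUC0-t and Cmax is the two-sided 90% interval, equivalent to two one-sided tests at 0.05, and naming the program that produces it. Confirm from the program or its output that 0.10 was used.

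The cost is a few characters of code, one sentence and a check of the output.
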